8 COVID-19 DETAILS

This study is conducted during the COVID-19 outbreak. The following data capture decisions have been taken due to national, local, or site-specific restrictions imposed due to COVID-19, with the primary need to prioritize the safety of clinical study teams and patients, and to maintain the integrity of the study/data collection.

- All protocol deviations relating to COVID-19 are collected.

- If Visit 2 is performed 8 weeks (56 days) or more after Visit 1, some Visit 1 assessments must be repeated.
- Visits 3 and 5 can be converted to remote visits (i.e. phone, video conference).
- Visits 4 and 6 can be postponed until the in-person visit is feasible and should be performed in person. Where applicable, remote data collection should be collected on the date of the original visit. The postponed Visits 4 and 6 will collect all data per protocol.

Currently, the impact of COVID-19 on the proposed statistical analyses is unknown. The statistical analysis already allows some flexibility for handling missing data, however, specific items/changes related to COVID-19 are being detailed in a separate document (Addendum 1), which will be maintained as a living document throughout the study continuation of the Parent phase and adjusted based on the duration and extent of the impact of the COVID-19 situation.

Note that no COVID-19 specific measures are taken for the Extension Phase.

9 DATA RECEIPT

All clinical eCRF data received from the Data Management provider per transfer agreement will be mapped to SDTM files. The information regarding minor/major violations will be received as excel file (a so-called “protocol deviations log”) and will be transferred to SDTM as well. The blinded results on the video-recordings (blinded rater’s CI-CS and CI-S) will be received from [REDACTED] as provider following the transfer agreement and will be mapped to SDTM. The received data will include relevant categorizations on missing data.

The SDTM files will be recoded to ADaM format, where necessary. Listings will be programmed on the SDTM and ADaM datasets, statistical analyses, tables, and figures will be programmed on ADaM datasets.

For all received data, a split will be made between data for the Parent Study and the data for the Extension Phase, to allow submission of the CDISC data and documentation for the Parent Study.

10 TECHNICAL DETAILS

10.1 Programming conventions

Programming conventions apply to both the Parent Study as well as the Extension Phase, unless otherwise specified.

Demographics

BMI will be calculated in SAS as follows: weight/height², with weight in kg and height in meter (unit kg/m²). Durations will be programmed as stated in the respective analysis sections. Where applicable, weight and height measurements will be converted to units cm and kg, using the following conversion factors: from inch to cm: multiply by 2.54, from lb to kg: multiply by 0.45359237. Variables with values representing a missing observation (such as -99, 99, 888 or 999) will be recoded to missing in SAS.

NPC Diagnosis

Time since diagnosis will be calculated as the difference in days between first dose date and the date of diagnosis +1. Date of diagnosis will be taken as the earliest date from the following two records: the (earliest) date of Medical History with MHDECOD= “Niemann-Pick Disease” and the date of genetic confirmation of disease as recorded in the Primary Genetic Diagnosis of NPC data.

If considered more feasible, the duration may be presented in weeks (calculated time divided by 7), months (calculated time divided by 365.25/12) or years (calculated time divided by 365.25) instead of days. For historical data however, it is likely that partial dates are available. If date of diagnosis is (partially) missing, the following will be applied:

- If only day is missing, the first day of the month will be used.
- If day and month are both missing, 1 January of the same year will be used.

If full date is missing, no imputation will be done.

Age calculation

Age at diagnosis will be based on the date of diagnosis (see above for determination) and the birth date as collected in the database. For a partial missing date of diagnosis, the rules as stated above will be applied. For partially missing birthdate: depending upon the level of precision of the collected birth date: if only month and year is available, then imputation of day 15 is used for calculation of age. If only birth year is available, 15 June of that year will be used as birthdate.

Age is not collected during the Extension Phase, therefore whenever age is necessary for any calculations or presentations at Visit 7, 8 or 9, it should be calculated using the respective visit date combined with the date of birth as collected at Visit 1. The same imputation rule as stated above (for calculation of age at diagnosis) will be applied.

Blinded data

The blinded results on the video-recordings (blinded rater's CI-CS and CI-S) will be received from [REDACTED] according to the agreed transfer specifications. Recoding needs to be done using the visit schedule provided with the blinded results, since the visit review order is randomly assigned. The LOCF for video comparison is already available in the [REDACTED] data.

SCAFI

For 8MWT, assistance of another person or using the wall as support is not allowed. However, timed 8MWT trials for participants who used “unallowable support” (another person or the wall) are entered in the database, considering these measurements are also necessary due to their relation to the primary and a number of secondary endpoints of the study based on videos of the test. Therefore, for the SCAFI analysis, the data for these patients that used either the wall or person support during the 8MWT should be made missing.

Furthermore, patients for 9HPT, the following clinical rules apply:

- if proband cannot complete trial in 5 minutes (i.e. 300 seconds) with dominant hand, move on to the trials with non-dominant hand
- if proband cannot complete one trial in 5 minutes (i.e. 300 seconds) with non-dominant hand, discontinue 9HPT

As a consequence, if in the database values >300 are entered for Trial 1 and/or 2, the approach for handling these data in regards to SCAFI will be:

- In the case Trial 1 has a value <300 and Trial 2 has a value of >300 seconds, only the trial 1 with value <300 will be used for further analysis.
- In the case Trial 1 has a value of >300 seconds and Trial 2 has a value of <300 seconds, the data will count as missing and unable to perform due to physical limitations (as per the discontinuation rules defined above, Trial 2 should not have been conducted)
- In other instances, where only one trial is performed with a value >300 seconds, or two trials are performed with both values >300 seconds, the data will be considered missing due to physical limitations and replaced with a missing value for further analysis.

After the adjustments made for 8MWT and 9HPT as above, SCAFI total score will be calculated as follows:

The mean of the trial1 and trial2 scores are determined for each subtest/hand, and referred to as:

8MW_avg, 9HPT-D_avg, 9HPT-ND_avg and PATA_avg. In case a subtest is only performed once, this value is taken as the mean. Then, the 8MW and 9HPT performance times are converted to the same dimension as the PATA rate, as follows: 8MW_recipr = 1/8MW_avg, 9HPT_recipr = (1/9HPT-D_avg + 1/9HPT-ND_avg)/2. Note that 8MW and 9HPT performance times cannot be 0.

Then each is converted into a Z-score using the following algorithms:

- 8MW_zscore = (8MW_recipr - BL(mean 8MW_recipr)) / BL(SD 8MW_recipr)
- 9HPT_zscore = (9HPT_recipr - BL(mean 9HPT_recipr)) / BL(SD 9HPT_recipr)
- PATA_zscore = (PATA_avg - BL(mean PATA_avg)) / BL(SD PATA_avg)

where BL means baseline value and SD means standard deviation. The mean 8MW_recipr and SD 8MW_recipr are determined using the SAF analysis population.

In case of missing values, the following applies:

- The cases with either 8MW, 9HPT (in one or both hands) or PATA tests not performed at all (“unable to perform due to physical limitations” or “not performed for other reason”) are excluded from the calculation of baseline means.
- Only when an 8MW score, 9HPT score or PATA score is missing due to “unable to perform due to physical limitations”, then a substitution will be applied as follows:
- When 8MW tests were not performed, then 8MW_recipr will be substituted by 1/1800 s.
- When 9HPT tests were not performed: if only data for one hand is missing, then 9HPT_avg=3000 s for that specific hand; when data for both hands are missing, then 9HPT_recipr=1/3000 s.
- When PATA tests were not performed, then PATA_avg is substituted with 0.

For agreement on “unable to perform due to physical limitations” or “not performed for other reason”, the sponsor will be contacted. The missings created for 8MWT and 9HPT as stated above are considered “unable to perform due to physical limitations”.

According to the “SCAFI rating manual”, the SCAFI total score is to be determined as the arithmetic mean of the 3 Z-scores. However, following explanation of IntraBio and [REDACTED] [REDACTED], the SCAFI score needs to be calculated as the mean of the non-missing Z-scores. The SCAFI score can only be determined if at least one test is actually performed, i.e.

in case all tests were imputed because of missing values, no SCAFI score will be determined. This contradicts the “SCAFI rating manual”.

SARA

The overall SARA score is reported as provided in the eCRF. For presentation of the subscore results, the individual results as provided in the eCRF will be used, where for the subscores finger chase, nose-finger test, fast alternating hand movements, heel-shin slide this is the average value for the two sides (left and right) as determined per eCRF.

mDRS

The mDRS composite score (only relevant for the Parent Study) is calculated as a sum of the separate subscores divided by 24. If one of the subscores is missing, the mDRS composite score is missing as well. As compared to the official questionnaire, the eCRF allows values of 0 (“normal”) for the subscores.

Modified NPC-CSS and ASIS

The modified (15 domain) NPC-CSS total score is calculated as the sum of the 8 major and the 7 modifier scores, and ranges from 0-54. This is referred to as the (15 domain) NPC-CSS sum/total score. The modified (5 domain) NPC-CSS consists of the domains for Ambulation, Cognition, Fine motor, Speech and Swallowing. The ASIS score is obtained by dividing the total (15 domain) NPC-CSS severity score of a patient by the age of the patient at Visit 9, providing a measure of the rate of disease progression in individual patients. The modified (15 domain) NPC-CSS total score, the modified (5 domain) NPC-CSS score and the ASIS score are all only relevant for the Extension Phase.

If one of the NPC-CSS subscores is missing, the total sum scores will be missing as well and so will the ASIS score.

Durations, determination of baseline values and handling of missing data will be programmed as stated in the respective analysis sections.

Laboratory

Laboratory safety data measurements that are denoted as smaller/larger than a certain value (e.g. < x.x), will be imputed with this value (e.g. x.x) for calculations of descriptive statistics. Listings will show the value as collected, and a footnote will be added to the summary tables for explanation.

Comments

The following data are either not collected or only collected as free text fields in the eCRF/database, or lack relevant information in the database, and it is therefore necessary that these details are added in the programming code manually. The decisions to drive this manual coding may be documented and finalized during the BDRM but can already be maintained/discussed during the course of the trial for efficiency.

- The reason for video unavailability is recorded as free text field, and it needs to be deducted if any of these reasons consider a “technical issue”. The sponsor will provide input.
- PATA score missing due to “unable to perform due to physical limitations” is not available as such in the database but needs to be deducted from a free comment field. The sponsor will provide input.
- Age is not collected during the Extension Phase and full birthdate is not provided in the Parent study; therefore, sponsor will provide details which patients turned 13

between Visit 7 and 8, and between Visit 10 and 11. Note that this may deviate from the age calculations performed for other presentations.

- SCAFI comments as stated above on SCAFI calculations. The sponsor will provide input to which comments relate to “unable to perform due to physical limitations” and which relate to “not performed for other reason”.
- Information to match the supplied bottles and/or sachets of study drug with the returned bottles and/or sachets, to be able to differentiate bottles/sachets used for the Parent phase and the Extension phase to allow appropriate compliance calculations.

Other

Durations, determination of baseline values and handling of missing data will be programmed as stated in the respective analysis sections.

Any other programming conventions that are not foreseen in preparation of this SAP, will be handled when encountered and documented separately.

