5.5.3 Baseline characteristics

The following relevant patient baseline characteristics will be listed and summarized overall (frequency and percentage) and are considered key subgroups. The subgroups differentiated on a median value will use the median value as determined for the specific analysis population.

- Naïve versus non-naïve as determined at screening
- Age (paediatric versus adult)
- Age/weight/dosing group
- Region (US versus EU)
- Selected Primary Anchor Test (9HPT-D or 8MWT)
- Patients on miglustat vs Patients not on miglustat at baseline visit (Visit 1 and/or Visit 2)
- Composite of SARA Subtests 1- 4 (Gait, Stance, Sitting, Speech): classification based on below (\leq)/above the median value at Visit 1.
- Intra-Patient variability between SARA score at Visit 1 (Baseline 1) vs Visit 2 (Baseline 2): classification based on below (\leq)/above the median value of the difference between the two visits.

- Intra-Patient variability between CI-S score (for primary anchor only) Visit 1 (Baseline 1) vs Visit 2 (Baseline 2): classification based on below (\leq)/above the median value of the difference between the two visits.
- Age of diagnosis: Early-infantile (<2 years), Late-infantile (2 to $<$ 6 years), Juvenile (6 to $<$ 15 years), Adolescent/Adult (\geq 15 years)
- Disease severity: classification based on below (\leq)/ above the median SARA score at Visit 1.

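### When only the year of diagnosis is known, the 1 January rule in SAP 10.1 makes age at diagnosis about half a year too young and time since diagnosis about half a year too long

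*SAP*

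**What the plan says.** SAP 10.1 (Programming conventions) has two sets of rules for partial dates.

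- **Diagnosis date.** "If only day is missing, the first day of the month will be used", and "If day and month are both missing, 1 January of the same year will be used".
- **Birth date.** "if only month and year is available, then imputation of day 15 is used for calculation of age", and "If only birth year is available, 15 June of that year will be used as birthdate".

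Both feed age at diagnosis. For the diagnosis side, the age calculation states: "For a partial missing date of diagnosis, the rules as stated above will be applied". The same imputed diagnosis date is subtracted from the first dose date to give time since diagnosis, which SAP 5.5.5 summarises under NPC-specific history. No lower bound at birth is given, and no rule for a negative result.

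The SAP expects these rules to be used. On diagnosis dates it says "For historical data however, it is likely that partial dates are available". In its comments on the database it adds that "full birthdate is not provided in the Parent study", without saying whether the birth month is available.

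The diagnosis date is the earlier of two records, a medical-history entry and the date of genetic confirmation.

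Age at diagnosis is a key subgroup in SAP 5.5.3, starting with "Age of diagnosis: Early-infantile (<2 years" and cut again at 6 and 15 years. It reappears for the extension phase in SAP 6.5.3. Under SAP 5.6 and 6.6 the subgroup displays are descriptive, with no statistical testing.

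**The concern.** An age is the difference of two dates. If one is moved to the start of its period and the other to the middle, the difference carries a systematic error that does not average out. Here the error always makes diagnosis look earlier. It would lower age at diagnosis, lengthen time since diagnosis and produce ages below zero. It would also move some patients across a subgroup boundary in one direction only.

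What is at stake is the accuracy of a reported baseline summary and of one key subgroup variable. With about 36 patients in the mITT set (SAP 2.4.1) spread over four age bands, one or two misplaced patients can visibly change a small cell.

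**Working it through.** The documents give no figure for this rule, so there is nothing of theirs to reproduce. The check assumes that birth and diagnosis days are each uniform over the calendar year.

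**Mean bias, year-only diagnosis.** The mean position of a uniform day, counted from 1 January, is day 182. Setting diagnosis to 1 January therefore moves it by -182 days. The birth rule shifts the birth date much less:

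- full birth date: 0 days
- month and year known, day 15 imputed: about -0.7 days
- year only, 15 June (165 days after 1 January): 165 - 182 = -17 days

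Bias in age is the diagnosis shift minus the birth shift:

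- full birth date: -182 - 0 = -182 days, or -182/365.25 = -0.50 years
- month and year: -182 + 0.7 = -181.3 days, or -0.50 years
- year only: -182 + 17 = -165 days, or -0.45 years

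Time since diagnosis uses the first dose date, so it is overstated by the whole 182 days, about 0.50 years.

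**Mean bias, only the day of diagnosis missing.** Day 1 moves the diagnosis date by -14.7 days on average. Age bias is -14.7 days with a full birth date, -14.7 + 0.7 = -14.0 days with month and year, and, in the simulation, +2.2 days with year only.

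**Diagnosis in the calendar year of birth, year-only diagnosis.** With both dates year-only, 1 January minus 15 June is -165 days (-166 in a leap year). With the birth month known, even a January birth gives 1 January minus 15 January = -14 days. Every such age is negative. It still falls below 2 years, which is the correct group.

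**Subgroup placement, year-only diagnosis.** Let k be a cut-point (2, 6 or 15). If diagnosis year minus birth year is not k, 1 January imputation does not move the patient across k. If it equals k, the true age is at least k in about half of cases, but the imputed age is always below k. About 50% of these patients are therefore misplaced, all into the younger group. A simulation of 400,000 date pairs compared this with a 15 June rule:

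| Birth date known to | 1 January rule | 15 June rule |
|---|---|---|
| month and year | 50%, all too young | 25% (13% too young, 12% too old) |
| year only | 50%, all too young | 50%, all too old |

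The share of all year-only diagnoses misplaced is half the share whose year difference hits a cut-point. It depends on the age distribution, which the documents do not give. Under assumed gamma distributions it was about 4 to 10% with the 1 January rule. With 15 June it was about 2 to 5% if the birth month is known, and not materially different from the 1 January rate if only the birth year is known. These ranges are indicative: more diagnoses near 2, 6 or 15 years would raise them, fewer would lower them.

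**In patients.** If all 36 mITT patients had year-only diagnosis dates, 4 to 10% is 36 × 0.04 = 1.4 to 36 × 0.10 = 3.6 patients. At 2 to 5% it is 0.7 to 1.8.

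**After a mid-period rule.** Mean bias in age falls from -181 to -16 days (birth month known) and from -165 to 0 days (both year-only). With the birth month known, about 25% of same-year diagnoses would still be negative, so a floor at birth is also needed.

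**The case against.** The strongest reply is that very little hangs on this. SAP 5.1 treats everything except the primary endpoint as exploratory, and the subgroup displays carry no tests. The number of partial dates is unknown, so the number of misplaced patients may be zero. SAP 10.1 says unforeseen programming conventions will be handled as they arise, and SAP 3.4 sends likely erroneous data to the blinded data review meeting. If only birth years are held, a mid-year rule reverses the direction of misplacement without reducing its rate. All of this stands and sets the size of the point. It does not justify the rule. Partial diagnosis dates are foreseen, and neither provision sets a floor at birth or removes the average shift.

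A reader might also infer more than the documents support:

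- *That the day-1 rule is as bad as the 1 January rule.* It is not; its mean bias is about two weeks or less.
- *That the mid-period birth rule causes the shift.* It is close to unbiased (about 17 days at most); the 1 January rule drives the error.
- *That negative ages will appear in summary tables or put patients in the wrong group.* The SAP tabulates age at diagnosis only as four categories, and a negative value lands in the correct one. It could appear in a listing or dataset.

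**Conclusion.** The point holds for diagnoses known only to the year. Age at diagnosis is too young by 0.45 to 0.50 years on average, same-year diagnoses compute as negative, and time since diagnosis is about half a year too long. These results rest on dates being roughly uniform within the year, and do not depend on the distribution of ages.

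Misplacement is confined to patients whose year difference is 2, 6 or 15, and is always towards the younger group. The 4 to 10% figure depends on assumed age distributions and applies to year-only diagnoses, not to all patients.

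The consequence is minor. It reaches the descriptive age-at-diagnosis displays in both study phases, listings, and the time-since-diagnosis summary. A reader might take it as a threat to the efficacy conclusion, but the primary one-sample test and the sample size do not use these dates. It is worth correcting because a stated rule gives a one-directional error that costs almost nothing to remove.

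**What to change.** Amend SAP 10.1 as follows.

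1. Impute partial diagnosis dates by the birth-date convention: day 15 when only the day is missing, 15 June when day and month are missing.
2. Bound the result: no earlier than the (imputed) birth date and no later than informed consent. The lower bound removes the remaining negative ages. The upper bound is needed because a 15 June date can fall after consent.
3. Where one of the two diagnosis records is complete and the other is imputed within the same year, use the complete one. The SAP does not say whether imputation precedes the choice of the earlier record; if it does, a 1 January imputation displaces a complete date later in that year.
4. Footnote the number of imputed diagnosis and birth dates in the age-at-diagnosis and time-since-diagnosis outputs.

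The cost is a few sentences in the SAP, a few lines of code and a footnote, with no new data. The change removes most or all of the mean bias in age whatever the birth-date precision. It roughly halves misplacement only if the birth month is held, so the SAP should also state which birth-date precision is available.

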6.1.2 Spinocerebellar Ataxia Functional Index (SCAFI)

The SCAFI consists of a timed 8MWT to be carried out at maximum speed, the 9-hole peg test with both dominant and non-dominant hands (9HPT-D; 9HPT-ND) and the "PATA" test to measure speech performance. For the 8MWT and 9HPT tests, a lower score/time indicates a clinical improvement. A higher "PATA" test score indicates improvement in speech performance [Schmitz-Hübsch et al, 2008].

The SCAFI represents vital movement features (8MWT;9HPD-D/-ND for evaluation of the coordination of the upper extremities; PATA-test for evaluation of speech). After the assessment, raw scores are transformed into reciprocals and converted into subtest Z-scores. The final SCAFI is then generated as the arithmetic mean of all three Z-scores.

Two subtests, the 9HPT-D and 8MWT, will be videoed in a standardized format at every visit, except Visit 0.

A subset of the SCAFI, the 9HPT-D, serves as an inclusion criterion for the severity of ataxia at the beginning of the study prior to enrollment.

The complete SCAFI will be performed at the time points designated on the schedule of events (Appendix 3A for "naïve" patients and Appendix 3B for "non-naïve" patients).

The score will be assessed by the investigator or qualified member of the study team.

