5.6.3 Additional secondary endpoints

All additional secondary endpoints will be presented using the mITT and PPS populations, and all individual data will be listed as well. No sensitivity analysis will be applied.

Measurement of Ataxia and Functioning

- SARA total score
- SCAFI total score
 - 9HPT-D
 - 9HPT-ND
 - 8MWT
 - PATA test

Descriptive statistics will be used to summarize the endpoints above at each visit.

The subscores of the SARA score (gait, stance, sitting, speech disturbance, finger chase, nose-finger test, fast alternating hand movements, heel-shin slide) will also be summarized for each visit using descriptive statistics. Stacked bar charts will be provided per visit, based on the subscores of the total SARA score.

Spaghetti plots of individual patient SARA total scores and the SCAFI total scores versus time will be made as well as a mean or median display versus time, depending upon the distribution, and corresponding two-sided 90% CI at each visit.

The average SCAFI subscores (8MW_avg, 9HPT-D_avg, 9HPT-ND_avg and PATA_avg) as determined according to Section 10.1, following the scoring manual, will also be summarized with descriptive statistics.

The changes in SARA total score, SCAFI total score, the SCAFI subscores (8MW_avg, 9HPT-D_avg, and PATA_avg) between Visit 2 and Visit 4, as well as the changes between Visit 4 and Visit 6 will be analysed using a one-sample t-test or a Wilcoxon Signed Rank test depending on the distribution of the data. The SCAFI subscore 9HPT-ND_avg will only be descriptively summarized in tabular format.

Measurement of Health-related Quality of Life

The results of EQ-5D-5L as well as the EQ-5D-Y will be combined into a 5-digit number presenting the health status of the subject. Frequency tables will be presented per visit for the 5 domains, as well as for the 5-digit number of the EQ-5D-5L and the EQ-5D-Y separately.

In addition, EQ-5D-5L and EQ-5D-Y domain percentages will be presented in separate bar charts per visit, with all visits combined into one plot (if possible).

The EQ-VAS score will be summarized by visit using descriptive statistics for patients aged < and \geq 18 years combined. Spaghetti plots of individual patient EQ-VAS scores versus time will be made as well as a mean or median display versus time, depending upon the distribution, and corresponding two-sided 90% CI at each visit.

Measurement of Overall Neurological Status

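### SCAFI averages whichever subtest Z-scores are available at each visit, so a tested change can compare two different composites when a subtest is missing for a non-physical reason

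*SAP*

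**What the plan says.** Protocol 6.1.2 defines the complete score: "The final SCAFI is then generated as the arithmetic mean of all three Z-scores". It says nothing about an incomplete one.

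SAP 10.1 fills that gap with three rules.

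- **Substitution.** "Only when an 8MW score, 9HPT score or PATA score is missing due to" inability for physical reasons is a value put in: 1/1800 s for the reciprocal walk time, 3000 s (or a reciprocal of 1/3000 s) for the peg test, 0 for PATA. Walks done with wall or personal support and peg tests over 300 s are first set to missing, then sent down the same route: "The missings created for 8MWT and 9HPT as stated above are considered" physical-limitation cases.
- **Averaging.** For anything still missing, "the SCAFI score needs to be calculated as the mean of the non-missing Z-scores". The SAP adds that this contradicts the rating manual.
- **Minimum.** "The SCAFI score can only be determined if at least one test is actually performed".

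SAP 5.6.3 sets the test: "The changes in SARA total score, SCAFI total score, the SCAFI subscores (8MW_avg, 9HPT-D_avg, and PATA_avg) between Visit 2 and Visit 4", and likewise from Visit 4 to Visit 6, "will be analysed using a one-sample t-test or a Wilcoxon Signed Rank test depending on the distribution of the data". For this group of endpoints, "No sensitivity analysis will be applied".

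SAP section 7, which collects the changes from the protocol, does not mention the SCAFI averaging rule.

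**The concern.** Each Z-score is centred and scaled on the group's baseline mean and SD, not on the patient's own level. A patient who walks poorly but handles pegs and speech at the group average has unequal Z-scores, and inclusion criterion 7b makes such profiles likely by admitting patients on either gait or the peg test. If one subtest is available at one visit and not at the other, the average is taken over different things, and the difference contains a term that has nothing to do with treatment.

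That term enters a quantity tested at both contrasts in roughly 36 patients, with no sensitivity analysis to reveal it. Incomplete visits are foreseeable: SAP section 7 records repeat visits where measurements could not be completed, and Protocol 10.4 allows alternative locations where an assessment may not be possible. Elsewhere SAP 10.1 is stricter: one missing component makes the mDRS or NPC-CSS total missing.

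**Working it through.** The plan gives no effect size, SD or power for SCAFI, so there is no figure of its own to reproduce. The rule can be followed through algebraically.

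**Inputs from the documents:** the averaging rule, the substitution rule and the one-test minimum (SAP 10.1); the tested contrasts (SAP 5.6.3); about 36 patients in the mITT set (SAP 2.4.1); one-sided 5% (SAP 5.1). **Assumed:** the Z-scores, the between-subtest correlation, the visit-to-visit noise and the number of patients affected.

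**Step 1: one patient, performance unchanged, subtest 1 dropped at the later visit.**

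Artefact = (Z2 + Z3)/2 − (Z1 + Z2 + Z3)/3 = [(Z2 + Z3)/2 − Z1]/3.

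| Z (8MWT, 9HPT, PATA) | All three | 8MWT dropped | Spurious change |
|---|---|---|---|
| −1.5, 0.2, 0.1 | −0.40 | +0.15 | +0.55 |
| −1, 0.5, 0.5 | 0.00 | +0.50 | +0.50 |
| +1, −0.5, −0.5 | 0.00 | −0.50 | −0.50 |
| 0, 0, 0 | 0.00 | 0.00 | 0.00 |

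The artefact can take either sign. It vanishes when the dropped Z-score equals the mean of the other two.

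**Step 2: typical size.** For unit-variance Z-scores with common correlation ρ, the variance is (1/9)[(1 + ρ)/2 + 1 − 2ρ] = (1 − ρ)/6. The SD is 0.41 at ρ = 0, 0.34 at 0.3, 0.29 at 0.5 and 0.26 at 0.6. If only one subtest remains, which the minimum rule permits, the artefact doubles: SD 0.82, 0.68 and 0.52 at ρ = 0, 0.3 and 0.6.

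**Step 3: effect on the group mean.** Two patients with the first profile give 2 × 0.55 / 36 = 0.03 baseline SD units.

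**Step 4: effect on the test.** Simulation with no true change, n = 36, ρ = 0.5, visit noise SD 0.3 per subtest, one-sided t-test, 6,000 replicates:

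| Patients without 8MWT at Visit 4 | Weakest walkers affected | Random patients affected |
|---|---|---|
| 1 | 7.0% | 5.2% |
| 2 | 8.7% | 4.6% |
| 3 | 12.2% | 5.1% |
| 5 | 15.9% | 5.2% |

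A repeat run of the weakest-walker case gave 6.9%, 9.6%, 11.8% and 16.7%. When the change used only subtests present at both visits, rejection was 4.8% to 5.2%.

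**The case against.** A reader might infer that weak walkers lose the walk test and so gain a better SCAFI. The documents do not support that. A patient who cannot walk, walks with support, or takes over 300 s on the pegs receives a very poor value, which lowers the score. Only non-physical missingness drops out, and no section ties that category to how a patient's subtests compare. The weakest-walker column above is therefore a conditional worst case, not an estimate of this trial's error rate.

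Frequency is also likely to be low. Protocol 3.1.2.5 does not allow the in-person Visits 4 and 6 to be skipped, and remote data collected in their place are entered as unscheduled visits. Remote Visits 3 and 5 lie outside the tested contrasts. Repeat visits recover some data. SAP 5.1 lets a Visit 1 value stand in for a missing baseline, though whether this works per subtest is not stated, and nothing similar covers SCAFI at Visits 4 or 6.

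SAP 5.1 treats everything but the primary endpoint as exploratory, with p-values only indicative. Three SCAFI subtests are tested separately and individual data are listed, so an artefact could be noticed. The averaging rule is deliberate, its conflict with the rating manual is stated, and it keeps patients in a small sample.

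All of this limits the size and direction of the problem. None of it makes the two visits comparable for an affected patient, and separate subtest results would expose a distorted composite without correcting it.

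**Conclusion.** The point holds as a defect in how the change score is defined. For a patient with different subtests available at the two visits, the tested change is not a change in one quantity. The result is certain as algebra; its size in this trial is not known. Under the assumed profile it is 0.55 for one patient and 0.03 on the mean for two of 36.

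The expected consequence is extra noise. Bias arises only if missingness for non-physical reasons is related to relative subtest performance. The documents neither show nor exclude that: the sponsor decides which category applies, partly from free-text comments, in an open-label study. It would be wrong to infer from this that the sponsor steers the result. SAP 10.1 says these decisions may be settled at the data review meeting, which SAP 3.4 asks to be blind to outcomes where possible.

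It would also be wrong to read this as a threat to the trial's main conclusion. The primary CI-CS analysis does not use SCAFI. Nor is the departure hidden: SAP 10.1 discloses the conflict with the manual. What is missing is an entry in section 7 against Protocol 6.1.2.

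**What to change.** In SAP 10.1 and 5.6.3, define each SCAFI change (Visit 2 to 4, Visit 4 to 6) as the difference between averages over the subtests that have a value, observed or substituted, at both visits of that comparison. Keep the existing requirement that at least one test was actually performed. Leave the change missing if no subtest is shared. Footnote the number of patients with fewer than three shared subtests for each contrast. Add to SAP section 7 that averaging over available subtests departs from Protocol 6.1.2.

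The by-visit summaries can keep the present rule. Patients with complete data are unaffected, no new data are needed, and the work is a few lines of text and a small derivation change.

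The cost is that, for a few patients, the tested change will not equal the difference between their by-visit scores, so the tables need a note. The fix also leaves one thing as it is: whether a missing subtest is labelled physical or other still decides between a very poor value and no value.
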